Cover Page for Protocol Summary Form

Official Study Title:	Multi-Level Trial of a Workplace Sales Ban of Sugary Beverages and Brief Motivational Counseling Intervention on Adiposity
NCT Number:	NCT ID not yet Assigned.
Document Date:	July 10, 2023

**SUTTER HEALTH
INSTITUTIONAL REVIEW BOARD**

Protocol Summary Form

Project Title: Multi-Level Trial of a Workplace Sales Ban of Sugary Beverages and Brief Motivational Counseling Intervention on Adiposity. The Sweet Study

Principal Investigator: [name], RD

Primary Sutter Contact Information:

Name: **[name]**

Email: [contact]

[contact]**

Protocol Summary Version Date: 6.30.2023

PART I: General Study Information

► Is there a **separate protocol document** (for example, an external study sponsor has supplied the protocol) that explains the study purpose, background/significance, inclusion/exclusion criteria, and data analysis/methods?

 Yes		Include protocol document with IRB application and skip to Part II.*
 No		Complete Part I and the rest of the form.

** In some cases, parts of the sponsor protocol will NOT be implemented at your site (for example, if the sponsor protocol allows for enrollment of minors but you will only be enrolling adults; or if the protocol is phase 1/2 but you will only be implementing the phase 2 part). If this is the case or there are other planned deviations from the sponsor protocol, please explain in the space provided in [Part IV: Other Comments] of this form.*

► **Note: If completing the below (Part I: General Study Information #1-7), please delete guidelines (in italics) when submitting your protocol to IRB.**

1. STUDY AIM/PURPOSE:

“Liquid sugar” in the form of sugar-sweetened beverages (SSBs, e.g., sodas, sports drinks, “fruit” drinks, bottled teas, coffees) has emerged as a dietary risk factor with potent harmful effects on metabolic health.¹⁻³ SSBs are the largest single source of added sugars in the American diet, and have disproportionate metabolic health impacts on lower-income and ethnic-minority Americans.^{4,5} We propose a double-randomized controlled trial of a multilevel workplace intervention that combines an employer-sponsored sales ban on SSBs with brief counseling to support reduced consumption.

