Brief SSB counseling interventions are promising but underutilized for obesity prevention. Brief interventions are short (~15 minute) counseling sessions that use motivational interviewing to offer advice and set goals to modify health behaviors. They are the standard of care for tobacco and alcohol prevention, with diverse applications in primary care,⁷ emergency rooms,⁸ and trauma centers,⁹ and are effective when delivered by nonmedical providers (e.g., probation officers,¹⁰ college counselors⁴⁰). Despite this track record, brief interventions have not been widely deployed in obesity prevention. Our literature review found only four smaller-scale studies examining the effectiveness of brief motivational interventions for SSB reduction.⁴¹⁻⁴⁴ All found that telephone or online brief counseling, with booster contacts using text messages or mobile apps, produce significant declines in SSB consumption and/or BMI. *Under Aim 1, we will conduct the first fully powered trial of brief counseling for SSB reduction in the context of a large employer.*

Workplace SSB sales bans have promise for obesity prevention, but studies are limited. A sales ban entails the removal of SSBs from all workplace sales outlets, replacing them with non-sugary beverage options while still allowing employees to bring SSBs from home. Informed by behavioral economics, sales bans are designed to “nudge” employees towards healthier options,^{44,45} while reducing the environmental cues and triggers that drive hedonic consumption.⁴⁶ There is robust prior research demonstrating that workplace sales bans on tobacco lead to declines in consumption and broader normative shifts.⁴⁸⁻⁵² Thus, a growing number of health systems, health departments, city governments, schools and universities have launched SSB sales bans.^{53 54-58} But evaluations are limited with as yet no published controlled trials.⁵⁹⁻⁶¹ In an observational study of 2556 employees, we found that a sales ban resulted in an average decline in employee SSB consumption of 1.5 oz/day.¹² In a subsequent microsimulation analysis, we estimated that SSB sales bans could save employers about \$300,000 per 10,000 employees over 10 years in healthcare savings and productivity gains.⁶² *Our proposed Aim 1*

**SUTTER HEALTH
INSTITUTIONAL REVIEW BOARD**

Protocol Summary Form

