Medical Record: Medical record data will be requested for the Sutter EHR (Epic) over a seven-year period (to include one year prior to enrollment, the 12-month study period and for five years thereafter). Data collection will include metabolic parameters related to obesity, such as: lipid panels, glucose, insulin, liver panels, height, weight, and past and prospective history. Medical records data collection will include medication history, progress reports, discharge summaries, and other data allowing us to look at the long-term impact of metabolic health in this population.

Depression: We will investigate the possible correlation between SSB consumption, general health and depression as well as change over time between the intervention and control campuses.

**SUTTER HEALTH
INSTITUTIONAL REVIEW BOARD**

Protocol Summary Form

Benefits: In cooperation with SutterSelect, we will obtain aggregate claim information for subjects at the intervention and control campuses. The aim of this data is to evaluate differences in health plan costs between the two groups. No individual health claims information will be collected. The data access form will review the security and privacy controls to ensure protections are in place. This data will be collected one year prior to enrollment, the 12-month study period and five years after.

Questionnaires: Subjects will complete all questionnaires remotely using a secure instance of REDCap.

BEVQ: BEVQ is a food frequency questionnaire measuring specific beverage items. We will use an adapted version of the BEV-Q field tested in the UCSF studies that captures beverage consumption while in the workplace and while not at work. The questions ask the type and frequency of consuming specific types of beverages on a typical day: regular/non-diet soda, diet soda, 100% fruit juice, fruit drinks (lemonade, smoothies), sports or energy drinks, sweetened coffee or tea drinks (Arizona iced tea, Frappucinos), and water. Participants also report how much (in ounces) they consume of each beverage each time over a limited, one week, recall period. Daily intake can be calculated for each beverage type by multiplying the frequency and serving size

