Copenhagen Burnout Inventory (CBI): The 6-item portion of the CBI assess personal burnout as is a state of prolonged physical and psychological exhaustion. Participants quantify the frequency of physical and emotional fatigue, as well as their susceptibility to illness, from on a six-point scale from "Always" to "Never". Formulated in a way that all human beings can answer it (regardless of job status), the measure was validated through the PUMA study.

Participant Randomization

Upon completion of five enrollment measurements (questionnaires, height/weight, waist, ASA24, and blood draw) participants will be randomly assigned to either a control group, or a group receiving a brief, remote motivational intervention, known as the Metabolic Health Improvement Plan (MHIP). Participants are randomized by a REDCap randomization module, using stratified random sampling by location. Those randomized to intervention will be contacted as described below.

SSB Brief Motivational Counseling Intervention- The Health Improvement Program

Participants randomly assigned to the health improvement program and will be contacted to participate in an education session with a trained coach via phone or video conference. The session led by a trained coach will describe the amount of sugar ingested in SSBs per week and will then proceed to provide personal guidance on health risks and the benefits of reducing sugar intake. Next, the coach will engage the participant in achievable, gradual goals to reduce SSB consumption reviewing and providing education materials. This will include discussing substitution beverages and preferred alternatives. Coaches will provide tools to the participant to increase self-efficacy and mediate the impact of stress, and cravings. The brief counseling session ends with the coach providing education materials including recordings relevant to the discussion, which can include topics of stress reduction and mindfulness. Depending on the participant, the brief intervention will take between 15 and 25 minutes to complete.

The coach will make two, 5-minute booster telephone calls within 4-6 weeks of the initial call. The first will be about two weeks after the initial session and the second call will be about two weeks later. The coach will revisit goals and obstacles and determine compliance to the educational materials.

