Using the Ecological Momentary Assessment (EMA) approach, cravings will be measured by study participants using smart phones. Using the REDCap platform, participants will receive a short set of questions at the following timepoints: baseline, 1, 2, and 3 months after SSB intervention starts at randomized affiliates, and 6 and 12-months. Two texts will be sent each day (morning and evening) four of the seven days of the week. Participants will be asked to quickly record the following: cravings (if any) for sugar sweetened beverages, psychological stress, consumption, and psychological stress. The primary target for this exploratory analysis is cravings for SSBs but we will also have access to information on whether or not subjects consumed SSBs in response to the craving. Each text should take one to-five minutes each. The content of the text is as follows:

- Introductory text at the start of each assessment period (Sunday afternoon) shall read:
 - o *Greetings Sweet Study Participant – this week, we’ll text you 4 clickable links in the morning and 4 in the evening on Tues, Thurs, Fri, and Sat. Each link will take 1-5 minutes to complete – Short and Sweet! The week after you finish the surveys, we’ll email you a \$10 gift code. Please complete at least 6 of the 8 texts in order to receive a gift code.*

Each day, the texts will be labeled as morning Sweet text 1, 2, 3, 4 and evening Sweet text 1, 2, 3, 4.

Location (asked in evening)

Today, were you physically working at your Sutter Health workplace?

**SUTTER HEALTH
INSTITUTIONAL REVIEW BOARD**

Protocol Summary Form

- Yes
- No

Can define a sugary drink here.

Craving Battery – Evening – Supplement and Parent

1. Today, did you crave a sugary drink? Yes / No

- If No, skip #2 and #3
- If Yes: Move on to #2.

2. At its most severe point, how strong was your craving for a sugary drink today?

Sliding bar, slider starting at middle or optimally nowhere and it gets placed when the respondent touches the screen, if starting in the middle then movement of bar required to advance to next question

**For #3, make these checkboxes, with the first two non-exclusive, and the “no” exclusive*

3. Did you drink anything in response to ANY of these cravings?

- Yes, a sugary drink
- Yes, water, a sugar-free drink, or a drink with no added sugar
- No

Psychological Stress Battery - Evening – Supplement and Parent

What was your overall mood like during the day?

1. I felt stressed, anxious, overwhelmed.

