Analytic Plan: We will analyze Aim 1 using all data collected at the baseline, 6- and 12-month time points. First, we will use ANOVA to compare group means and determine whether there is a significant main effect for each intervention (the sales ban and the brief intervention). Based on theory and our previous studies, we know that baseline risk factors and demographics are likely relevant to the impact of these interventions; those at greater baseline risk tend to benefit more from the interventions. Therefore, each dependent variable will also be examined using a linear regression model, which allows us to observe the main effects of these factors. For example, the model predicting HOMA change would include assignment to the sales ban condition (coded as 0/1), assignment to the brief intervention condition (coded as 0/1), baseline HOMA, baseline SSB consumption, baseline BMI, race/ethnicity, and sex. Subsequent models can consider baseline BMI > 25, ethnicity and job classification. The procedure for analyzing each outcome would be the same, but with each primary and secondary outcome substituted for HOMA in turn.

For SSB consumption, we will examine at-work consumption, at-home consumption, and total consumption as separate outcomes to thoroughly investigate the impact of the interventions across work and home environments. We will similarly check for potential compensatory consumption in sugar from calories and total calories for participants in the intervention conditions relative to controls. If ASA-24-based total calories or calories from sugar disproportionately increase in the intervention groups, this suggests a compensatory effect.

Although we believe our strategy of cluster randomization and controlling for individual differences that can vary regionally (such as ethnic distribution) is sufficient, we will also analyze the effects of the brief intervention via an exploratory mixed regression model, with individuals nested within sites, to see if study site was an important factor. If it is, we will consider mixed models where possible.

**SUTTER HEALTH
INSTITUTIONAL REVIEW BOARD**

Protocol Summary Form

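### As described, the BevQ has one sports/energy line with no sugar-free counterpart; if that line counts as SSB, a switch within it goes unrecorded and pulls the secondary SSB effect toward zero

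*Combined protocol and SAP*

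**What the plan says.** The BEVQ paragraph in section (4b), Procedures, describes an adapted questionnaire, field tested in the UCSF studies, that covers intake at work and away from work. Its lines are "regular/non-diet soda, diet soda, 100% fruit juice, fruit drinks (lemonade, smoothies), sports or energy drinks", then "sweetened coffee or tea drinks (Arizona iced tea, Frappucinos), and water". The scoring rule is: "Daily intake can be calculated for each beverage type by multiplying the frequency and serving size".

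Section 1 defines the exposure as "SSBs, e.g., sodas, sports drinks" and further types, so sports drinks are SSBs by the protocol's own definition. Energy drinks are not named there, but they share the sports drink line.

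On the interventions, section 3 (Significance) describes the ban as removing SSBs from sale and "replacing them with non-sugary beverage options while still allowing employees to bring SSBs from home". The counseling description in (4b) says of the session: "This will include discussing substitution beverages and preferred alternatives".

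In (4c), the Aim 1 analytic plan states that "we will examine at-work consumption, at-home consumption, and total consumption as separate outcomes". SSB consumption is a secondary outcome (section 1), and 12-month SSB consumption is the outcome Y in the Aim 3 mediation model.

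**The concern.** The list marks sugar status for soda and for coffee and tea, but not for sports and energy drinks. A sugar-free sports or energy drink has nowhere to go except the line that also holds the sugared product. Both interventions aim to move people from sugared drinks to other drinks, so a questionnaire that cannot see one such move may under-record response in the arms where response is expected.

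At stake are the between-arm SSB comparisons and the Aim 3 SSB outcome. A safeguard is also involved. Under Aim 1, Anticipated Problems, the plan relies on anthropometric and blood measures agreeing with the SSB changes as reassurance about self-report. If some true reduction is invisible to the BevQ, biomarkers could improve while recorded intake does not, and that check becomes harder to read.

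**Working it through.** The plan states no figure that depends on this item, so there is none to reproduce. The check applies the protocol's own scoring rule to its own list.

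**1. Which lines carry sugar status**

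| BevQ line | Sugar status marked? | Sugar-free counterpart? |
|---|---|---|
| Soda | yes | yes (diet soda) |
| Coffee or tea | yes (sweetened only) | none listed |
| Sports or energy | no | none listed |

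**2. One participant.** Assume 20 oz once a day; the volume is illustrative. Score per line = frequency × ounces.

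- Sugared energy drink to sugar-free energy drink: 1 × 20 = 20 before and 1 × 20 = 20 after, on the same line. Recorded change 0; true SSB change −20 oz/day.
- Regular soda to diet soda: the regular line goes from 20 to 0 and the diet line from 0 to 20. Recorded SSB change −20, which is correct.
- Sugared energy drink to water: the sports/energy line goes from 20 to 0. Recorded SSB change −20, which is correct.

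Only switching within the sports/energy line is lost.

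**3. If the line is left out of the total.** No section says which lines are summed. Leaving this one out does not solve the problem: sugared sports drinks, which section 1 counts as SSBs, would then be missed, and a participant who gave them up would score 0 before and 0 after.

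**4. From participant to arm comparison.** Let D be the true between-arm difference in SSB reduction, and let S_I and S_C be the mean oz/day switched within the line in the intervention and control arms. Then

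recorded difference = D − (S_I − S_C) = D × (1 − q), where q = (S_I − S_C)/D.

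If switching is equal in the arms, q = 0 and there is no bias. If it is more common under intervention, the recorded effect shrinks. The documents give neither q nor the share of intake from sports and energy drinks, so q is assumed:

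| Assumed q | Share of D recorded | If D were 4.2 oz/day |
|---|---|---|
| 0.1 | 90% | 4.2 × 0.9 = 3.78 |
| 0.2 | 80% | 4.2 × 0.8 = 3.36 |
| 0.3 | 70% | 4.2 × 0.7 = 2.94 |
| 0.5 | 50% | 4.2 × 0.5 = 2.10 |

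The 4.2 oz/day is the 6-month difference from the current Sutter Health trial (section 2) and serves only as a scale. It is itself a self-reported figure and may already contain the same loss.

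**5. Is it corrected elsewhere?** No follow-up item, scoring exclusion or linked data source is described that would take sugar-free sports or energy drinks out of the total. The study does draw the distinction in another instrument: item 3 of the evening craving battery offers "Yes, water, a sugar-free drink, or a drink with no added sugar" as a response separate from a sugary drink.

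**The case against.** The strongest objection is that the questionnaire itself is not shown. The BEVQ paragraph is a short summary, and the item as worded may already restrict the line to sugared products. That is fair, and it makes the point conditional. But the summary marks sugar status elsewhere and not here, and no section says which lines form the total.

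Second, the 24-hour recall (ASA24) is collected at baseline, 6 and 12 months, and the arms are compared on total calories and calories from sugar. A switch to a sugar-free product should lower the latter, so the trial is not blind to this substitution. This stands as a partial check. It is one recall per wave, and the plan uses it to look for compensation, not as the source of the work, home and total SSB outcomes.

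Some stronger readings are tempting but not supported:

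- A reader might infer that both interventions promote sugar-free sports or energy drinks. Neither description names them. What is supported is that such switching is plausible and probably more common under intervention.
- A reader might discount the pilot's 8.2 and 25.4 oz/day declines and conclude that the sample is too small. Those are self-reported declines from a pilot without an untreated control group. If the pilot used this questionnaire, they already include the loss and would be discounted twice. No sample-size shortfall follows.
- A reader might infer treatment-dependent error in the baseline SSB covariate. Baseline questionnaires are completed before individual randomization, so counseling cannot have affected them; misclassification there mainly costs precision.
- A reader might extend the point to smoothies, which share a line with lemonade. Nothing in the documents suggests that participants would switch between sweetened and unsweetened smoothies.

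**Conclusion.** The concern holds in a limited form. As the BevQ is described, and if the sports/energy line is summed into SSB intake, a switch to a sugar-free product within that line is scored as no change. If this switching is more common in the intervention arms, the secondary SSB-consumption effect and the Aim 3 SSB outcome are biased toward zero. The direction follows from the list, the scoring rule and that assumption. The size cannot be estimated from the documents; the table above shows only what assumed shares would imply.

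The primary outcomes are not measured by the BevQ and are not affected. The bias runs toward no effect, so it would hide an SSB reduction rather than create one. The change is worth making because it is nearly free and must be in place at baseline: if the baseline wave is collected unsplit, BevQ data cannot recover the distinction later.

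**What to change.** At baseline, 6 and 12 months, and for both work and home, split the line into sugar-sweetened sports or energy drinks and sugar-free sports or energy drinks, as is already done for soda. State in (4c) that SSB consumption is the sum of the sugar-sweetened lines, and list them. Keep the combined sports/energy line as a derived sum, so that the total used in the UCSF studies can still be calculated for comparison.

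If the item as fielded already excludes sugar-free products, a sentence in the BEVQ paragraph saying so, with the list of summed lines, settles the point.

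The cost is one extra line per setting at each wave, hence a slightly longer form, and a small departure from the field-tested version.

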To assess the effectiveness of this multilevel intervention, called the workplace *Metabolic Health Improvement Program (MHIP)*, we will conduct a double-randomized trial in partnership with the clinical trials division of a large Northern California-based academic healthcare system, Sutter Health ($N=700$ employees on $N=16$ hospital campuses). We will first cluster-randomize 8 Sutter Health hospital campuses to the SSB sales ban condition and 8 campuses to serve as controls (no sales ban). Across these 16 campuses, we will further randomize heavy-SSB-consuming employees (>30 oz/week) to receive a brief SSB counseling intervention delivered remotely or to a control condition.^{11,12} The **primary outcomes** are central obesity (e.g., waist circumference) and change in serum insulin sensitivity (homeostatic model assessment [HOMA] ratio). **Secondary outcomes** include changes in SSB consumption, Body Mass Index (BMI), and lab values to include: lipid profile, triglycerides, triglyceride:HDL ratio, uric acid, ApoA, ApoB, lactate, ALT/AST, GGT, fasting glucose, fasting insulin, HbA1c. We will assess dietary composition remotely using the Automated Self-Administered 24-hour (ASA-24) at baseline, 6 and 12 months, and waist circumference remotely with empirically validated instructions and a standardized tape measure provided to participants. We will collect blood samples in the workplace labs at baseline and 12 months. All analyses will consider compensatory changes in at-home SSB intake, calories from sugar, and total calories. Aims are:

Aim 1: How well does each intervention work alone? We will assess the independent effects of the brief counseling intervention and workplace SSB sales ban on changes in primary and secondary outcomes. We will compare outcomes across employees exposed to the brief intervention only ($n=175$), SSB sales ban only ($n=175$), and no intervention ($n=175$). *We hypothesize that the brief counseling intervention and sales ban will each independently decrease waist circumference and HOMA relative to no intervention. Those at high risk (baseline BMI >25 , ethnic-minority, and lower-occupational status) will benefit more from the interventions.*

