statistically significant mean reduction of 4.2 oz/day in SSB consumption in employees at intervention sites versus controls ($p < .04$), including a 2.7 oz/day reduction in SSBs consumed while at work ($p < 0.02$). *This study is not cluster-randomized nor does it consider serum biomarkers for metabolic disease, which the proposed study will address. However, it demonstrates a successful collaboration with Sutter Health, and shows the feasibility of the proposed recruitment and remote data collection efforts.*

3. SIGNIFICANCE:

The proposed study tests a scalable, efficient approach for obesity prevention in the workplace. Following recent trials demonstrating the effectiveness of online obesity counseling using nonmedical providers, we test a remote counseling intervention delivered by trained health coaches.^{38,39} The SSB sales ban is a food environment intervention that is easily adopted through changes in procurement policy and that promotes health equity by impacting the workforce as a whole.

Across all aims of the proposed study, we will assess the heterogeneity of intervention effects across higher-risk employee groups from ethnic minority backgrounds, lower occupational status and >25 baseline BMI. A recognized limitation of this study is that our disparities analyses will be confined to people in the workforce. If the interventions tested here prove effective, however, future studies can test them in other congregate settings that touch populations outside the labor market (e.g., in criminal justice settings, community colleges).

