***Patient-Reported Outcomes Measurement Information System (PROMIS):** We have selected a self-report measures of depression which are person-centered which all study participants will be asked to complete. We will investigate the possible correlation between SSB consumption, general health and depression as well as change over time between the intervention and control campuses. Subjects who report high levels of depression will be provided with contact information to Sutter Health's Employee Assistance Program (EAP). No documentation will be placed in the subject's medical or employment record.

REDCap will be set-up with a notification alerting the CRCs when the depression scores result with severe depression. When the participant completes their questionnaires, the Clinical Research Coordinators will review the depression questionnaire. If a participant scores a severe depression (score, a phone call will be made to the participant using a script. A form has been created and will be used as documentation. This includes a script for leaving a message and for a live call. During a live call only, the Clinical Research Coordinator will inform the participant of their high score and will with the phone number to Sutter Health's EAP.

Demographics: Including gender, ethnicity, primary work location, occupational status, income, and usual number of worked shifts each week will be recorded via REDCap.

Medical History: Concurrent medications and general medical history will be obtained directly from study participants with an emphasis on metabolic history such as diabetes. Data will be recorded via REDCap

Height, weight, and waist circumference measurements: Subjects will be asked to record their self-reported height in REDCap. Height and weight will be measured using a standard scale with an attached stadiometer in a semi-private location at the affiliate and record their weight and height in REDCap. A tape measure and instructions on measuring waist will be sent to the participant's home. They will record the measurement in REDCap.

Fasting Blood Draw: A fasting blood draw will take place at the draw station of the local affiliate. Labs will be drawn at baseline and at 12-months. The panels will be comprised of metabolic and lipid panels that pertain to metabolic syndrome. Labs will be accessible to participants using My Health Online.

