The Automated Self-Administered 24-hour Dietary Assessment Tool (ASA24): The ASA24 is a free, web-based tool that enables multiple, automatically coded, self-administered 24-hour diet recalls and/or single or multi-day food records. ASA24 was developed by the National Cancer Institutes. Participants will be asked to complete one 24-hour recall at enrollment, 6 and 12 months using a link and password sent to them.

The Stanford Leisure-Time Categorical Item (L-CAT): The L-CAT is a questionnaire asking participants to rank their activity level from inactive to very active. This tool has been validated and can detect statistical differences when used over time.

Patient-Reported Outcomes Measurement Information System (PROMIS) Depression: The PROMIS Depression 4-item questionnaire banks assess self-reported negative mood (sadness, guilt), views of self (self-criticism, worthlessness), and social cognition (loneliness, interpersonal alienation), as well as decreased positive affect and engagement (loss of interest, meaning, and purpose). The depression short forms are universal rather than disease specific. All assess depression over the past seven days. If they score in the severe range the Clinical Research Coordinators will contact the participant and will provide them with the EAP contact information and will encourage them to call EAP.

Food Craving Questionnaire-Trait, Reduced (FCQ-T-r): The 15-item FCQ-T-R assesses (1) preoccupation with SSB (i.e., obsessive thought about food and eating), (2) loss of control (i.e.,

**SUTTER HEALTH
INSTITUTIONAL REVIEW BOARD**

Protocol Summary Form

difficulty regulating eating behavior when exposed to food cues), (3) positive outcome expectancy (i.e., believing eating to be positively reinforcing), and (4) emotional craving (i.e., tending to crave food when experiencing negative emotion).

Reward Based Eating Drive (Red-13): The 13-item RED assesses three aspects of drive to eat (loss of control, lack of satiety, and preoccupation with food). Items are answered on a Likert scale from 0 (Strongly Disagree) to 5 (Strongly Agree). Example items include "I feel out of control in the presence of delicious food" and "When I start eating, I just can't seem to stop."

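### One ASA-24 recall per visit, on an unspecified day with no on-site record, leaves the ban's sugar and calorie contrasts averaged over an unknown mix of on-site and off days

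*Combined protocol and SAP*

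**What the plan says.** The ASA24 paragraph in (4b) states: "Participants will be asked to complete one 24-hour recall at enrollment, 6 and 12 months using a link and password sent to them". The schedule table in the same section lists ASA 24 at baseline, 6 and 12 months and shows no repeat recalls. Nothing sets the day of the week, balances working days against days off, or asks whether the recalled day was worked.

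The recall has a definite job. Section 1 commits the trial as follows: "All analyses will consider compensatory changes in at-home SSB intake, calories from sugar, and total calories". The Aim 1 analytic plan in (4c) gives the reading rule: "If ASA-24-based total calories or calories from sugar disproportionately increase in the intervention groups, this suggests a compensatory effect".

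The ban is tied to a place. Section 3 describes it as clearing workplace outlets of sugary drinks, "replacing them with non-sugary beverage options while still allowing employees to bring SSBs from home".

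The example Aim 1 regression contains the two assignment indicators and "baseline HOMA, baseline SSB consumption, baseline BMI, race/ethnicity, and sex". Other outcomes are to be handled in the same way, and no separate model is written out for the ASA-24 quantities.

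Three neighbouring items bear on work pattern:
- Under Demographics, "usual number of worked shifts each week will be recorded via REDCap".
- The evening text asks "Today, were you physically working at your Sutter Health workplace".
- BevQ separates drinks taken at work from drinks taken elsewhere.

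**The concern.** The ban changes what is sold on campus, so its effect on a day's diet should depend on whether that day was spent on campus. One recall sees one day. If that day was a day off, the recall shows eating at home and none of the direct removal of drinks at work. If it was a working day, the recall shows both. The arm mean therefore mixes two kinds of day in proportions that the trial does not set and will not know.

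The supporting analysis of dietary compensation is at stake. ASA-24 is the only planned instrument that covers food as well as drink, so the checks on sugar calories and total calories rest on it. A null result could mean no compensation, or a day mix in which it was hard to see. An apparent rise would be ambiguous in the same way. The natural follow-up, comparing the on-site-day effect with the off-day effect, cannot be made. Unrecorded day type also adds noise to change from baseline.

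**Working it through.** The plan states no sample size, standard deviation or detectable difference for any ASA-24 outcome, so there is no figure to reproduce. The check has three parts.

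**1. Do the other measures close the gap?**
- *BevQ* has the work/non-work split, but for beverages only. It cannot show sugar or calories from food.
- *Usual shifts per week* describes the person, not the recalled day.
- *The evening on-site item* runs on four of seven days in an assessment week, with no stated link to the ASA-24 date.

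None of them says whether the recalled day was worked.

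**2. What does the ban contrast estimate?** Let p_B and p_C be the shares of recalls that fall on on-site days at ban and control campuses. Let Δ_on and Δ_off be the ban effects on the two kinds of day, and m_on and m_off the mean control intakes. Then

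expected contrast = p_B·Δ_on + (1 − p_B)·Δ_off + (p_B − p_C)·(m_on − m_off).

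If p_B = p_C = the true on-site share, this is the average-day effect and is unbiased. If the shares are equal but unrepresentative, the first two terms are wrongly weighted. If the shares differ by arm, the last term adds a spurious difference.

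**3. How large could it be?**

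*Wrong weighting, in ounces of sugary drink.* Section 2 reports that the current Sutter trial found a fall of 4.2 oz/day, "including a 2.7 oz/day reduction in SSBs consumed while at work". The remainder is 4.2 − 2.7 = 1.5 oz/day outside work. Assume that both figures are weekly averages, that the 1.5 oz is spread evenly over all days, and that there are d on-site days a week. The at-work fall on an on-site day is then 2.7 × 7/d, and the recalled effect is 1.5 + p × (2.7 × 7/d).

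| d (assumed) | On-site day | Off day | Share p (assumed) | Recalled effect | Against 4.2 |
|---|---|---|---|---|---|
| 3 | 1.5 + 6.3 = 7.8 | 1.5 | 3/7 (true share) | 1.5 + 2.7 = 4.2 | 0% |
| 3 | 7.8 | 1.5 | 0.20 | 1.5 + 1.26 = 2.76 | −34% |
| 3 | 7.8 | 1.5 | 0.70 | 1.5 + 4.41 = 5.91 | +41% |
| 5 | 1.5 + 3.78 = 5.28 | 1.5 | 5/7 (true share) | 1.5 + 2.7 = 4.2 | 0% |
| 5 | 5.28 | 1.5 | 0.40 | 1.5 + 1.51 = 3.01 | −28% |

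The values of d and p are chosen for illustration and are not document figures. The outcome is ounces of drink, used only because the documents give a work/non-work split for nothing else.

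*Arm difference in day mix, in calories.* The documents give no calorie difference between on-site and off days. If it were 50 to 200 kcal and the on-site share differed by 10 points between arms (both assumed), the spurious difference would be 0.10 × 50 = 5 to 0.10 × 200 = 20 kcal.

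**The case against.** The strongest reply is that nothing here shows bias. All participants get the same link procedure, and no section suggests that recalled days are skewed or that the skew differs by campus. Part 2 of the working shows that a representative day mix leaves the group contrast unbiased and only noisier. This stands. A reader might infer that the arms are not comparable, or that participants pick whichever day suits them. The documents support neither: they are silent on how and when the link is answered. For counseling the inference is weaker still, because individuals are randomized within location and day mix is balanced in expectation before follow-up.

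Second, the percentages concern ounces, for which the plan has a dedicated instrument in BevQ. This also stands, and it is why they are illustrations only. They shrink if off-campus effects are larger. Under Aim 1, (4c) cites an unpublished at-home fall of 9.3 oz/day in heavy drinkers. Putting 9.3 in place of 1.5 (which mixes two studies, and a before/after figure with a controlled one) gives a weekly mean of 9.3 + 2.7 = 12.0. The three scenarios become 10.56 (−12%), 13.71 (+14%) and 10.81 (−10%).

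Third, a reader might infer that the problem cannot be repaired afterwards or that compensation would go unseen. That goes too far. Shifts are collected at all three visits and the evening item runs in the same assessment periods, so partial sensitivity analyses are possible. A recall of an on-site day also captures eating at home that day, and at-home drink intake comes from BevQ.

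What remains is that the day mix is neither controlled nor recorded, so representativeness would have to be taken on trust.

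**Conclusion.** The point holds in a limited form. The ASA-24 sugar and total-calorie contrasts for the ban are averages over an unknown mix of on-site and off days. They are unbiased for an average day only if recalled days are representative in each arm. The plan neither secures this nor allows a direct check, and it cannot separate the two kinds of day.

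The reach is the supporting compensation analysis. Waist circumference, HOMA and the BevQ at-work and at-home results do not depend on it. The size in calories is unknown. The range of 2.8 to 5.9 oz against 4.2 shows only how the mechanism works under assumed recall shares and assumed on-site days. The documents do not establish that the ban estimate is biased. The case for change is that a better method is available at small cost.

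**What to change.** 1. For every ASA-24 recall, at all three visits, ask the item already written for the evening text, "Today, were you physically working at your Sutter Health workplace", reworded to refer to the recalled day.
2. Send ASA-24 links on randomly chosen days, by the same procedure in all arms, aiming for on-site and off days in proportion to the participant's usual shifts.
3. Include the on-site indicator in the ASA-24 models. Add its interaction with the ban as a supporting analysis, because the split will be imprecise with one recall per visit and 16 campuses.
4. Report the shift-weighted weekly effect, with the on-site-day and off-day effects beside it.

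The cost is a link schedule, one extra question and two model terms, and some links will have to be re-sent. Under Participant Randomization, ASA24 is among the measurements to be completed before assignment, so a missed baseline day should be replaced promptly by another so that randomization is not held up. The change keeps one recall per visit. It addresses day mix and does not remove the imprecision of a single recall.
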